7.4 User Preference Questionnaire

Prior to each treatment phase completion, the participant will be asked to complete a short questionnaire on their experience with the PureWickTM System or the Hollister® FUP. The questionnaire is designed to assess the following:

- Comfort with PureWick[™] FEC/PureWick[™] Urine Collection System or the Hollister[®] Female Urinary Pouch External Collection Device
- Ease of use in placing and removing the PureWickTM FEC and the Hollister[®] Female Urinary Pouch External Collection Device

After completing both treatment phases for the study, the participant will complete the preference questions on their experience with the PureWickTM System and the Hollister® FUP. The survey is designed to assess the following:

• The participants preferred device after using both the PureWick[™] FEC/PureWick[™] Urine Collection System and the Hollister® Female Urinary Pouch External Collection Device.

7.5 Participant Follow-Up

After all procedures are complete in both treatment phases, the participant will be discharged from the study. The participant will be asked to report any discomfort or voiding issues occurring within the first 24 hours after discharge from the study to the PI or sponsor.

7.6 Replacement of Participants

A participant that discontinues from the study will be replaced when feasible.

8.0 PARTICIPANT DISCONTINUATION/WITHDRAWAL

8.1 Discontinuation/Withdrawal

- A participant may withdraw from the study at any time at his/her own request or may be withdrawn at any time at the discretion of the investigator or sponsor for safety, behavioral, compliance, or administrative reasons. This is expected to be uncommon.
- At the time of discontinuing from the study, no further assessments will be performed.
- If the participant withdraws consent for disclosure of future information, the sponsor may retain and continue to use any data collected before such a withdrawal of consent.
- Participants who withdraw or discontinue the study early may be replaced.

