7.2.13 Days 23-28

1. Same procedures as days 2-7.

7.2.14 Day 29

- 1. Same procedures as days 2-7 with the exception of steps 6 and 7.
- 2. Participant to complete 4-week N-QOL assessment.
- 3. Participant to complete Day 29 PROMIS Sleep Disturbance assessment.
- 4. Participant to complete comfort and ease of use questionnaires.
- 5. If this day is the last day of phase 1 treatment for the participant, they will begin washout and prepare for phase 2 treatment.
- 6. If this day is the last day of phase 2 treatment for the participant, they will complete the study. Participant is to complete the End of Study Preference Survey.

7.2.15 Day 30

The participant will be asked to report any discomfort or voiding issues occurring within the first 24 hours after treatment phase completion or discharge from the study to the PI or sponsor. Skin assessments will also be conducted 24 hours after the participant completes the treatment phase and/or the study.

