7.3 Safety Assessments

7.3.1 Draize Scale

For each daily visit (described in 7.2-7.7), skin condition will be evaluated by nurses using the Draize scale (Table 1). Skin assessments will also be conducted 24 hours after the participant completes the study, either in person or virtually.

If during the skin assessment a Draize score of 4 is documented on the skin irritation scale in any category, it must be recorded as an AE and will require participants to discontinue from the treatment phase. Any other score on the skin irritation scale in any category may be recorded as an AE based on PI discretion.

To assess a potential AE identified during the home visit, the nurse will contact the PI or designee. The site will document the AE assessment on the appropriate CRF from and follow the AE until resolution. If the PI requests a follow up visit with the participant, this can be conducted on site or virtually per investigational site policy.

However, if the AE is not resolved during the treatment phase(s) within 4 weeks from the AE start date, the participant will be discontinued from the study.

Also, if during the skin assessment a Draize score of 2 or greater is documented for the device placement site, a photograph may need to be taken of the skin in the anatomical area of device application. The photo will be sent in a pseudonymized matter to the site, only the subject ID and the date when the picture was taken will be collected. These photographs will be shared with the Principal Investigator / Sub-Investigator, the Sponsor, and the study staff only and will be used for the Principal Investigator / Sub-Investigator / Sub-In

| Score | Erythema (redness) | Edema (swelling) | Bleeding |
|------------------------------|--|---|--|
| 0 | None | None | None |
| 1 ^{a} | Very slight (barely perceptible) erythema | Very slight (barely perceptible) skin surface rise | Just a visible spot of red |
| 2^a | Well-defined erythema | Well-defined skin surface rise (edges of area well-defined by definite raising) | A drop of red blood |
| 3 ^{a} | Moderate erythema | Moderate skin surface rise | A continuing ooze of red blood |
| 4 ^{b} | Severe (beet red) or damage to skin (eschar formation) | Severe skin surface rise | Significant bleeding from the sight |

 Table 1: Draize Scale for Skin Irritation

^{*a*} = Represents irritation in any category and may require participant's removal from the study based on PI decision.

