9.0 ADVERSE EVENTS AND DEVICE DEFICIENCIES

9.1 Definitions of Events

9.1.1 Adverse Events (AEs)

An AE is defined as any untoward medical occurrence, unintended disease or injury, or untoward clinical signs (including abnormal laboratory findings) in participants, users or other persons, whether or not related to the investigational device and whether anticipated or unanticipated (ISO14155:2020). This definition includes events related to the investigational device, the comparator or the procedures involved.

Pre-existing conditions should be considered as part of the participant's medical history and should not be reported as an AE unless there is a substantial increase in severity or frequency of the condition, which has not been attributed to natural history. Likewise, planned hospital visits and/or hospital stays should not be considered as adverse events. Exacerbation of an existing condition should be reported as an AE if the event meets the protocol definition of an AE.

The clinical course of the event will be followed according to accepted standards of medical practice until the event resolves, stabilizes, or in the opinion of the Investigator, is no longer considered clinically significant. The Investigator must supply the Sponsor with information concerning the follow up and/or resolution of the AE.

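### Protocol 8.1 ends all assessments at study discontinuation, while 7.3.1, 9.1.1 and 9.4 require an open adverse event to be followed and its outcome recorded

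*Protocol*

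**What the plan says.** Four parts of the protocol bear on what happens to an AE that does not clear.

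- **7.3.1 (Draize Scale), follow-up duty.** "The site will document the AE assessment on the appropriate CRF from and follow the AE until resolution". No time limit is given.
- **7.3.1, 4-week rule.** A few lines later: "if the AE is not resolved during the treatment phase(s) within 4 weeks from the AE start date, the participant will be discontinued". The sentence goes on to make clear that this means discontinuation from the study, not only from the treatment phase.
- **8.1 (Discontinuation/Withdrawal).** "At the time of discontinuing from the study, no further assessments will be performed". The section covers withdrawal by the investigator or sponsor for safety as well as withdrawal at the participant's request. It makes no exception for an open AE.
- **9.1.1 and 9.4.** 9.1.1 says: "The clinical course of the event will be followed according to accepted standards of medical practice until the event resolves, stabilizes", or until the investigator judges it no longer clinically significant, and obliges the investigator to send follow-up information to the sponsor. 9.4 requires start date, end date and outcome on the eCRF for every AE.

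On skin checks after device use ends, 7.2.15 (Day 30) says: "Skin assessments will also be conducted 24 hours after the participant completes the treatment phase and/or the study". Section 7.3.1 ties the same check to completing the study. In the Schedule of Activities (1.3) the Draize row has no mark in the washout column.

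**The concern.** The 4-week rule selects events that have not resolved, and study discontinuation then brings 8.1 into play. A site that applies 8.1 as written stops assessing a woman at the point where her AE has proved persistent. A site that applies 7.3.1, 9.1.1 and 9.4 keeps going. Both can claim to follow the protocol, so AE follow-up could differ between sites and countries in a study of about 30 women.

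What is at stake is the recorded outcome and duration of the most persistent events, and the oversight of women who leave the study with an open injury. Skin safety is one of the two primary questions, and the pilot is meant to inform how often nurses need to visit in the later randomised trial. How long skin events last is relevant to that use.

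A related gap concerns the 24-hour skin check. It is worded for a participant who completes a phase or the study, so it is unclear whether a woman stopped early gets one.

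**Working it through.** The plan gives no statistical figure on this point, so the check sets the passages side by side and then counts days.

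**Step 1. Side-by-side reading for an AE open 4 weeks after onset**

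| Section | Instruction |
|---|---|
| 7.3.1, follow-up sentence | Keep following until resolution |
| 7.3.1, 4-week sentence | Discontinue from the study |
| 8.1 | Stop assessments at study discontinuation |
| 9.1.1 | Keep following until resolved, stable or not clinically significant; inform the sponsor |
| 9.4 | Record end date and outcome |

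Rows 2 and 3 together end assessment; rows 1, 4 and 5 require it to continue. No passage exempts AE follow-up from 8.1, and none gives an order of precedence.

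**Step 2. Other routes into 8.1.** The footnotes to Table 1 in 7.3.1 allow removal from the study for scores of 1 to 3 at the investigator's decision, and require removal from the treatment phase and/or the study for a score of 4. Where removal is from the study, 8.1 applies while irritation is still present, possibly well before 4 weeks. Where it is from the phase only, 8.1 does not apply and 7.2.7 sends the woman into washout.

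**Step 3. When the 4-week mark falls.** An AE starting on phase Day k reaches 4 weeks on Day k + 28. The first visit after a night of wear is Day 2 and the last such visit is Day 29.

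- Day 2: 2 + 28 = Day 30. Day 29: 29 + 28 = Day 57.
- *Phase 1, 2-week washout (Days 29-42, Phase 2 baseline Day 43).* k + 28 ≥ 43 when k ≥ 15. Onsets on Days 2-14 reach the mark on Days 30-42, mostly within washout. Onsets on Days 15-29 reach it on Days 43-57, at or after the baseline visit, where a Draize check is scheduled.
- *Phase 1, 4-week washout (baseline Day 57).* Onsets on Days 2-28 reach the mark on Days 30-56, before that baseline.
- *Phase 2.* The mark falls on Day 30 or later. Under 7.2.14 and 7.5 the woman has by then completed treatment and been discharged, or is about to be. Planned contact ends through 7.5, not 8.1.

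The conflict with 8.1 therefore acts mainly on AEs that begin in Phase 1.

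**Step 4. Scheduled skin checks in between.** After a completed Phase 1, the Draize row runs to Day 30 and resumes at the Phase 2 baseline: 43 − 30 = 13 days to 57 − 30 = 27 days without a scheduled score. After an early stop for a score of 4, washout begins at once. If the Day 30 check does not apply, the interval is the whole washout of 14 to 28 days.

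**Step 5. Effect on the analysis.** Protocol 10.5.2 and SAP 5.2.2.2 define the primary safety endpoint as the mean of daily Draize scores during each phase. Follow-up after discontinuation does not enter it. SAP 7.0 presents AEs by phase, assigns washout AEs to the Phase 1 device, and describes no analysis of duration or resolution.

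**The case against.** The strongest answer is that 8.1 refers to scheduled study assessments and leaves the safety duties of section 9 intact. Section 9.1.1 has no exception for discontinued participants, 9.4 wants an end date and outcome for all AEs, and 7.3.1 lets the investigator request an AE follow-up visit on site or virtually. A woman stopped for a score of 4 has an AE recorded by rule, and the follow-up duty applies to her in washout. The SAP's schedule also shows AE review as a continuing row. All of this stands. It makes continued follow-up a fair reading, but it does not make it the stated one: 8.1 is unqualified, and AE review is not a skin assessment.

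Several stronger readings are tempting, and the documents do not support them.

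- *Outcomes will be lost.* That is the literal consequence of 8.1, not a certainty, for the reasons just given.
- *Harms will look shorter or more reversible.* An AE that triggers the rule is open at 4 weeks, so it would be recorded as ongoing and at least 4 weeks long. Its duration is censored; it does not appear resolved.
- *Almost all onset days are affected.* In Phase 2 the route is discharge under 7.5, and an AE that heals by Day 30 is seen at the daily visits. In Phase 1 the answer depends on washout length, as the day count shows.
- *The rule ends participation for any unrelated slow-healing event.* The sentence sits in the Draize section, after text on AEs found at home visits, and carries the qualifier "if the AE is not resolved during the treatment phase(s) within 4 weeks from the AE start date". Its scope is ambiguous, so this consequence is conditional.

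**Conclusion.** The contradiction is real and limited. Sections 7.3.1 and 8.1, read together and literally, stop assessment of AEs that are unresolved by definition, against the follow-up sentence in 7.3.1, against 9.1.1 and against the fields required by 9.4. Strict follow-up to resolution is required by 7.3.1 only; 9.1.1 also accepts stabilisation or loss of clinical significance, which is itself a small mismatch.

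The possible loss is the final outcome and duration of such AEs, and oversight of the women concerned. The primary safety endpoint and the planned AE summaries by phase do not depend on it. The size cannot be given as a count: the documents state no AE rate and no distribution of duration, and with about 30 participants the number may be small or zero. Whether the 24-hour skin check applies after an early stop is unclear.

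This rests on two assumptions: that 8.1 is applied to the 4-week discontinuation as worded, and that no site instruction outside these documents already settles the matter.

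**What to change.** The sponsor should reconcile the passages in one protocol amendment:

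1. Bring 8.1 into line with 7.3.1, 9.1.1 and 9.4, so that the text states whether AEs open at study discontinuation continue to be followed and their outcome recorded, and up to what end point.
2. State whether the 24-hour skin check in 7.2.15 and 7.3.1 applies when a phase or the study is stopped early, and make the Draize row of the schedule agree.
3. State which AEs the 4-week rule in 7.3.1 covers, and what its reference to the treatment phase(s) means for an AE that runs into washout.

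Which clinical rule applies is for the sponsor to decide. The cost is wording. If the sponsor's answer is that follow-up continues, it adds some in-person or virtual contacts for the women who leave with an open AE. No change to sample size, endpoints or the primary analysis is needed.

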8.2 Lost to Follow-Up

A participant will be considered lost to follow-up if she repeatedly fails to keep the visit schedule or is unable to be contacted by the study site or nurses.

The following actions must be taken if a participant fails to keep the visit schedule or is unable to be contacted:

- The site and nurse must attempt to contact the participant and reschedule the missed visit as soon as possible and counsel the participant on the importance of maintaining the assigned visit schedule and ascertain whether or not the participant wishes to and/or should continue in the study.
- Before a participant is deemed lost to follow up, the investigator or designee must make every effort to regain contact with the participant. Where possible, 3 telephone calls and, if necessary, a certified letter to the participant's last known mailing address or local equivalent methods. These contact attempts should be documented in the participant's study record.
- Should the participant continue to be unreachable, she will be considered to have withdrawn from the study.

9.0 ADVERSE EVENTS AND DEVICE DEFICIENCIES

9.1 Definitions of Events

9.1.1 Adverse Events (AEs)

An AE is defined as any untoward medical occurrence, unintended disease or injury, or untoward clinical signs (including abnormal laboratory findings) in participants, users or other persons, whether or not related to the investigational device and whether anticipated or unanticipated (ISO14155:2020). This definition includes events related to the investigational device, the comparator or the procedures involved.

Pre-existing conditions should be considered as part of the participant's medical history and should not be reported as an AE unless there is a substantial increase in severity or frequency of the condition, which has not been attributed to natural history. Likewise, planned hospital visits and/or hospital stays should not be considered as adverse events. Exacerbation of an existing condition should be reported as an AE if the event meets the protocol definition of an AE.

The clinical course of the event will be followed according to accepted standards of medical practice until the event resolves, stabilizes, or in the opinion of the Investigator, is no longer considered clinically significant. The Investigator must supply the Sponsor with information concerning the follow up and/or resolution of the AE.

9.1.2 Serious Adverse Events (SAEs)

A serious adverse event is defined by ISO 14155 and/or 21 CFR 803.3 as an adverse event that led to:

- a. Death,
- b. Serious deterioration in the health of the participant, users, or other persons as defined by one or more of the following:

- a life-threatening illness or injury, or
- a permanent impairment of a body structure or a body function including chronic diseases, or
- in-patient or prolonged hospitalization, or
- medical or surgical intervention to prevent life-threatening illness or injury, or permanent impairment to a body structure or a body function,
- c. Fetal distress, fetal death, a congenital abnormality, or birth defect including physical or mental impairment.

NOTE: Planned hospitalizations for a preexisting condition, or a procedure required by this trial without serious deterioration in health, is not considered an SAE.

9.1.3 Adverse Device Effect (ADE) / Serious Adverse Device Effect (SADE)

An adverse device effect is defined as any adverse event that is considered to be related to the use of an investigational medical device. This definition includes any event resulting from insufficiencies or inadequacies in the instructions for use, deployment, implantation, or operation or any malfunction of the investigational device and includes any event that is a result of a user error, intentional misuse of the investigational medical device and/or comparator if the comparator is a medical device.

A serious adverse device effect (SADE) is defined as an ADE that has resulted in any of the consequences characteristic of an SAE. An anticipated serious adverse device effect (ASADE) is an effect which by its nature, incidence, severity or outcome has been identified in the risk assessment.

9.1.4 Unanticipated (Serious) Adverse Device Effect (UADE/USADE)

An unanticipated (serious) adverse device effect (UADE/USADE) is any (serious) adverse device effect on health or safety or any life-threatening problem or death caused by, or associated with, an investigational device, which by its nature, incidence, severity, or outcome has not been identified in the current instructions for use and/or current version of the risk analysis report, or any other unanticipated serious problem associated with a device that relates to the rights, safety or welfare of participants.

Anticipated serious adverse device effect (ASADE) is an effect which by its nature, incidence, severity or outcome has been identified in the risk assessment.

A sponsor shall immediately conduct an evaluation of any unanticipated adverse device effect.

UADEs/USADEs will be reported to FDA as required by 21 CFR Part 812 and ISO 14155:2020 and will be reported to the appropriate governing body per ISO 14155:2020.

9.2 Severity of Adverse Events

Each AE shall be assessed for its severity, or the intensity of an event, experienced by the participant according to the criteria below.

| Severity Rating | Description |
|-----------------|---|
| Mild | Event, signs, or symptoms that do not interfere with the participant's daily activity, are usually considered self-limiting, can be treated with non-prescription type medications, and do not require medical intervention |
| Moderate | Event may interfere or cause low level inconvenience with the participant's daily activity. Requires medical intervention and/or treatment; however, unlikely to require hospitalization or be considered potentially life-threatening in nature |
| Severe | Event may cause significant discomfort to the participant and/or interferes with the participant's daily activity. Requires medical intervention and/or treatment to preclude a permanent impairment; may be life threatening and/or require hospitalization |

9.3 Relationship of Adverse Event to Device(s)/Procedure

Each AE will be assessed for its relationship to the investigational device or procedure according to the following guidelines.

- A. Assess each AE for its relationship to the device or procedure.
 - Device Related: This category should be restricted to AEs directly attributable to the PureWickTM System and Hollister[®] Female Urinary Pouch External Collection Device during the urine capture assessments.
 - Procedure: A procedure includes any study-related activity performed during the set-up or application of the PureWickTM System and Hollister[®] Female Urinary Pouch External Collection Device and/or urine capture assessment procedure.
- B. To assess the causality, clinical judgement should be used and the relevant study documentation, such as the study protocol should be consulted. The presence of confounding factors, such as concomitant medication/treatment, underlying diseases, other concurrent illness or risk factors should also be considered. The above considerations apply also to the serious adverse events occurring in the comparison group.

Each SAE will be classified according to four different levels of causality:

- 1. Not Related
- 2. Possible
- 3. Probable
- 4. Causal Relationship

| Relatedness | Description |
|-------------|---|
| Not Related | Relationship to the device, comparator or procedures can be excluded when: the event has no temporal relationship with the use of the investigational device, or the procedures related to application of the investigational device; the serious adverse event does not follow a known response pattern to the medical device (if the response pattern is previously known) and is biologically implausible; the discontinuation of medical device application or the reduction of the level of activation/exposure - when clinically feasible - and reintroduction of its use (or increase of the level of activation/exposure), do not impact on the serious adverse event; the event involves a body-site or an organ that cannot be affected by the device or procedure; the serious adverse event can be attributed to another cause (e.g. an underlying or concurrent illness/ clinical condition, an effect of another device, drug, treatment or other risk factors); the event does not depend on a false result given by the investigational device used for diagnosis, when applicable; |
| Possible | The relationship with the use of the investigational device or comparator, or the relationship with procedures, is weak but cannot be ruled out completely. Alternative causes are also possible (e.g. an underlying or concurrent illness/ clinical condition or/and an effect of another device, drug or treatment). Cases where relatedness cannot be assessed, or no information has been obtained should also be classified as possible. |
| Probable | The relationship with the use of the investigational device or comparator, or the relationship with procedures, seems |

| | relevant and/or the event cannot be reasonably explained by another cause. |
|------------------------|--|
| Causal Relationship | the serious adverse event is associated with the investigational device, comparator or with procedures beyond reasonable doubt when: the event is a known side effect of the product category the device belongs to or of similar devices and procedures; the event has a temporal relationship with investigational device use/application or procedures; the event involves a body-site or organ that the investigational device or procedures are applied to; the serious adverse event follows a known response pattern to the investigational device application (or reduction of the level of activation/exposure) and reintroduction of the level of activation/exposure) and reintroduction of its use (or increase of the level of activation/exposure), impact on the serious adverse event (when clinically feasible); other possible causes (e.g. an underlying or concurrent illness/ clinical condition or/and an effect of another device, drug or treatment) have been adequately ruled out; harm to the subject is due to error in use; the event depends on a false result given by the investigational device used for diagnosis when applicable; In order to establish the relatedness, not all the criteria listed above might be met at the same time, depending on the type of device/procedures and the serious adverse event. |

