9.4 Reporting of Events

For all adverse events, all sections of the appropriate electronic Case Report Form (eCRF) must be completed including AE start and end date, outcome of AE, severity, seriousness, relationship to device and relationship to the procedure. All AEs shall be promptly reported to the Sponsor.

For European site(s):

• All SAEs, SADEs, UADEs/USADEs, and Serious Health Threats must be reported to the Sponsor via completion of the appropriate eCRF no later than 3

calendar days of the site/investigator becoming aware of the event. If the study team is unable to access the electronic data capture system, the event may be reported to the Sponsor by emailing [contact].

• De-identified copies of all requested relevant documentation should be submitted to the Sponsor within 72 hours of knowledge, as appropriate.

For U.S. site(s):

- All SAEs, SADEs, UADEs/USADEs, and Serious Health Threats must be reported to the Sponsor via completion of the appropriate eCRF within 1 working day of the site/investigator becoming aware of the event. If the study team is unable to access the electronic data capture system, the event may be reported to the Sponsor by emailing [contact].
- De-identified copies of all requested relevant documentation should be submitted to the Sponsor within 72 hours of knowledge, as appropriate.

In the US, it is the responsibility of the Investigator to report adverse events to individual Institutional Review Boards (IRBs) and/or regulatory authorities according to the local regulations.

In Europe, it is the responsibility of the Sponsor to report adverse events to individual Ethics Committees (ECs) and/or regulatory authorities according to the local regulations in each participating country.

- For the purpose of this guidance and based on the definitions above, the following events are considered sponsor reportable events in accordance with MDR Art. 80(2):
 - a) any serious adverse event that has a causal relationship with the investigational device, the comparator or the investigation procedure or where such causal relationship is reasonably possible;
 - b) any device deficiency that might have led to a serious adverse event if appropriate action had not been taken, intervention had not occurred, or circumstances had been less fortunate;
 - c) any new findings in relation to any event referred to in points a) and b).

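### Protocol 9.3 defines device-related AEs more narrowly than 9.1.3 and grades causality for SAEs only, so non-serious or later-appearing device harms could be coded as unrelated

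*Protocol*

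**What the plan says.** Protocol 9.1.3 defines an ADE as "any adverse event that is considered to be related to the use of an investigational medical device". It expressly takes in use error and inadequate instructions, and it sets no time window.

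Protocol 9.3 opens with all AEs in scope: "Each AE will be assessed for its relationship to the investigational device or procedure according to the following guidelines". Its device guideline then reads "This category should be restricted to AEs directly attributable to the PureWickTM System" and the Hollister "Female Urinary Pouch External Collection Device during the urine capture assessments". The separate procedure guideline covers "any study-related activity performed during the set-up or application of the PureWickTM System" and the Hollister pouch, together with the capture assessment procedure. Neither guideline names overnight wear.

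The graded scale follows: "Each SAE will be classified according to four different levels of causality". The levels are Not Related, Possible, Probable and Causal Relationship. The rule that an unassessable case counts as Possible sits inside that scale.

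Protocol 9.4 requires relationship to device and to procedure on the eCRF for every AE. It also sets a fixed clock: "All SAEs, SADEs, UADEs/USADEs, and Serious Health Threats must be reported to the Sponsor via completion of the appropriate eCRF", within 3 calendar days for European sites and 1 working day for U.S. sites. SAP 7.0 presents AEs and SAEs by treatment phase, and its text contains no split by relatedness.

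**The concern.** Sections 9.1.3 and 9.3 A answer the same question differently, and 9.3 A is the one written as an instruction to the assessor. The devices are worn overnight during sleep for 28 days per phase. Weighing is done by the nurse at the next day's visit, and the last skin check comes on Day 30, after capture has ended. A rule tied to an undefined capture window may therefore miss harm that arises in use or shows itself later. For non-serious events, the only device criterion offered is direct attribution, with no intermediate level for a doubtful link.

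Three things depend on the relationship code:

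- **Reporting.** Protocol 9.1.4 puts seriousness in parentheses, so an unanticipated ADE need not be serious to be a UADE. It calls for immediate sponsor evaluation, and 9.4 sets the fixed clock. A non-serious event coded unrelated keeps only the general duty of prompt reporting.
- **Monitoring.** Protocol 12.2 directs monitors to device-related AEs, UADEs and SAEs, and 9.6 provides no safety committee. For a non-serious AE, relatedness is what brings it within that wording.
- **Consistency.** The trial is open-label and meant to support reimbursement. Any device-related count would depend on how each assessor reads 9.3 A.

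**Working it through.** No arithmetic applies: the plan gives no figure on this point, and none can be derived. The check sets the sections side by side.

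**1. Scope of the definition.** Compare 9.1.3 with 9.3 A under the two possible meanings of the capture window.

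| Event | 9.1.3 | 9.3 A, window = nurse's weighing visit | 9.3 A, window = overnight capture |
|---|---|---|---|
| Irritation starting during overnight wear | ADE if considered related | Outside | Inside if directly attributable |
| Skin finding first seen on Day 30 | ADE if considered related | Outside if the window governs when the event appears | Outside if the window governs when the event appears; may be inside if it governs the causing exposure |
| Event from use error or poor instructions | Expressly included | Not mentioned | Not mentioned |

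The documents do not settle which column applies. Protocol 7.2.7 has used pads bagged on waking and weighed at the visit, which fits the first meaning. The second is equally open, because the night is what is being assessed.

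**2. The Day 30 case.** Protocol 7.2.15 provides a skin assessment and asks for discomfort or voiding issues in the 24 hours after a phase ends. The Schedule of Activities has no device wear or urine measurement that day. If the window governs when an AE appears, a Day 30 finding is outside it on either meaning. SAP 7.0 assigns washout AEs to the Phase 1 device if it was used, so the SAP itself does not confine attribution to capture.

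**3. Scope of the scale.** Two events with the same faint link to the device are treated differently:

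- Serious event: Possible under the 9.3 scale. If the link cannot be assessed at all, it is again Possible.
- Non-serious event: no level is assigned. The assessor must still complete the 9.4 field, with direct attribution as the only stated criterion.

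A Draize score of 4 that does not meet the SAE definition is a concrete example. Protocol 7.3.1 makes it a mandatory AE, but 9.3 gives it no graded causality.

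**4. What depends on the code.** The ADE and UADE labels, the 9.4 clock for unanticipated events and the 12.2 monitoring category depend on it. The primary safety endpoint (mean daily Draize score, Protocol 10.5.2 and SAP 5.2.2.2) and the AE presentation in the SAP 7.0 text do not. The table shells (SAP Appendix 1) are not shown, so a relatedness table can be neither confirmed nor excluded.

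**The case against.** The strongest reply is that this is loose wording without a demonstrated effect. If the window meant the weighing visit, the device-related category would be almost empty, which the authors can hardly have intended. Non-serious AEs are not left unassessed, since 9.3 and 9.4 require a relationship judgement for each one. All AEs go promptly to the sponsor, and 9.1.4 reaches problems associated with the device as well as those caused by it. Irritation (both devices) and rash and abnormal discharge (the pouch) are in the protocol's own risk table. They therefore look anticipated and are weak examples of a lost UADE. A four-level scale for SAEs also fits the SAE reporting rule in 9.4.

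Much of this stands, and it limits the point. A reader might infer that overnight harms are excluded and are in fact under-classified. The documents do not support that, because the window is undefined and one plausible meaning includes the night. A reader might also equate direct attribution with the Causal level and estimate what share of events would be lost. Nothing in the protocol makes that equation, and no AE distribution is given. Nor do the documents say that nearly all harms will be non-serious: the risk table includes choking, strangulation and electrical shock.

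What the reply does not remove is the contradiction. Section 9.3 A sets a restriction that 9.1.3 lacks, and the missing scale for non-serious AEs is explicit in the text.

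**Conclusion.** The point holds as an inconsistency that should be corrected. Protocol 9.3 A is narrower than 9.1.3, its time window is undefined, and the causality levels with their default to Possible are stated for SAEs only. Followed as written, non-serious device harms and harms appearing outside capture could be coded as not device related. They would then lose ADE status and, where unanticipated, UADE status and the 3-calendar-day or 1-working-day clock.

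The size cannot be calculated. It depends on how assessors read 9.3 A and on how many AEs have a doubtful link or appear late. If every AE is plainly related or plainly unrelated and appears during capture, little changes. The primary Draize endpoint and total AE counts by phase are unaffected, and the sponsor still receives every AE. The conclusion assumes that sites apply 9.3 A as the working rule, and it is subject to the eCRF code list and SAP table shells, which are not shown.

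**What to change.** 1. In Protocol 9.3 A, delete the direct-attribution restriction and the capture-assessment window. Define device related in line with 9.1.3, for example: *an AE judged related to use of the study device, whenever it appears*. Keep set-up and application under the existing Procedure field so that the two eCRF fields stay distinct.
2. In Protocol 9.3 B, apply the four levels, including the default to Possible, to each AE instead of each SAE. The level descriptions that refer to the serious event need the same edit.
3. If device-related AEs are tabulated under SAP 7.0, state that the count is Possible or higher.

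The cost is protocol and SAP wording and an eCRF code list, since relationship is already a required field. Events already coded would need a relationship check against the revised definition. The downside is somewhat higher device-related counts for both devices.
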